2.3 Exploratory Objectives

| Exploratory Objectives |
|---|
| 1. To assess relationships between serial FET PET and clinical outcome (benign TRC and recurrence) in patients with recurrent metastatic lesions, recurrent high grade gliomas and recurrent low grade gliomas. |
| 2. To determine if MRI can differentiate between benign treatment- related changes and recurrence. |
| 3. To describe the distribution of the standardized uptake value (SUV) and tumor-to-background ratio (TBR) for observed lesions. |
| 4. To determine if FET PET can differentiate between benign TRC and recurrent metastatic lesions. |
| 5. To determine if FET PET can accurately differentiate between low-grade and high-grade gliomas in population 2. |

3 Study Design

3.1 Characteristics

This is a prospective, Phase 2, single center, open-label study in patients with intracranial neoplasms. Eligible participants will undergo baseline assessments at enrollment. All study participants will undergo a single FET PET study. Repeat FET PET will be offered to adult patients and not in pediatric patients.

3.2 Stopping Rules

For pediatric patients, patients will be reviewed after imaging, and if inappropriate patient management is instituted based upon the results of the 18F-FET PET imaging, then we will suspend enrollment of pediatric patients until the case is reviewed with the FDA and the neurooncology site committee.

3.3 Number of Subjects

It is anticipated that 199 patients over four years will be enrolled in this study.

3.4 Eligibility Criteria

Patients must have baseline evaluations performed prior to the administration of the radiopharmaceutical and must meet all inclusion and exclusion criteria. In addition, the patient must be thoroughly informed about all aspects of the study, including the study visit schedule and required evaluations and all regulatory requirements for informed consent. The written informed consent must be obtained from the patient prior to enrollment. The following criteria apply to all patients enrolled onto the study unless otherwise specified.

Patients participating in other clinical trials will be eligible for this study including patients undergoing surgery guided by 5-aminolevulinic acid.

3.4.1 Inclusion Criteria

1. Presence or suspicion of intracranial neoplasm in two populations:
 - a. Population 1: patients after primary treatment (radiation therapy and/or surgery) with suspicion of recurrence on MRI. Three sub-populations will be considered:
 - i. Recurrent metastatic lesions
 - ii. Recurrent high-grade gliomas (Grades 3 and 4)
 - iii. Recurrent low-grade gliomas (Grades 1 and 2)
 - b. Population 2: patients prior to primary treatment with planned biopsy or surgical resection.
2. Age > 3 years.

3.4.2 Exclusion Criteria

1. Patient with known incompatibility to PET or CT/MRI scans.
2. Patient unlikely to comply with study procedures, restrictions and requirements and judged by the Investigator to be unsuitable for study participation.

- a. Sedation or anesthesia can be used for patients who cannot tolerate the exam.

3.5 Discontinuation of Study Intervention

Study drug will be given per protocol, unless any of the following discontinuation criteria are met:

- Unacceptable adverse event(s);
- Participant decides to discontinue study drug (with or without concurrent withdrawal of informed consent);
- Significant participant non-compliance with protocol;
- If the participant meets an exclusion criterion (either newly developed or not previously; or, recognized) that precludes further study drug administration.
- General or specific changes in the participant's condition render the participant unacceptable for study drug administration in the judgment of the investigator.

Participants will be discontinued from study drug administration when any of these criteria apply. The reason for discontinuation, and the date the participant discontinued (defined as the later date of decision to discontinue drug or last dose) must be documented in the case report form (CRF). Participants removed from study for unacceptable adverse events will be followed as described in Section 7.3. Participants who do not receive study drug will be replaced.

3.6 Duration of Follow Up

Patients will be in follow-up until their planned biopsy or surgery is performed to correlate imaging findings with histology. Follow-up will be performed off study, and there are no study specific related procedures that are required after the imaging study. If patients do not undergo biopsy or surgery, we will review imaging that was performed as clinical standard of care to determine if the lesion has grown as part of the secondary aims.

3.7 Study Discontinuation/Withdrawal

Participants will be discontinued/withdrawn from study participation when any of the following criteria apply:

- Completion of study intervention and follow-up per protocol
- Lost to follow-up
- Withdrawal of consent for data submission
- Death
- Study termination

The reason for discontinuing study participation and the off-study date must be documented in the case report form (CRF).

Participants may withdraw from the study at any time and for any reason at their own request or at the request of their legally acceptable representative. Participants will be asked for reason(s) of withdrawal and presence of any AEs for documentation in the CRF. If possible, the participant will be seen and assessed by the Investigator and AEs followed according to protocol.

The study may be terminated early for any reason, which may include, but is not limited to:

- Changes in the benefit-risk assessment
- Decision to stop manufacturing study drug

In the event of early study termination, follow up medical records collection may occur, as described in Section 3.6, for participants who remain on study at that time. Investigators will be notified of any additional steps that are necessary to protect participants' interests. Investigators must notify the IRB and other applicable stakeholders, in accordance with local laws and regulations.

3.8 Study Timeline

3.8.1 Primary Completion

The study will reach primary completion 48 months from the time the study opens to accrual.

3.8.2 Study Completion

The study will reach study completion 60 months from the time the study opens to accrual.

4 Study Drugs

4.1 Description, Supply and Storage of Investigational Products

4.1.1 Investigational Drug #1

O-(2-[¹⁸F]fluoroethyl)-L-tyrosine (FET) is a radiopharmaceutical that will be produced under cGMP by a research pharmacist certified and highly experienced in the Department of Radiology and Biomedical Engineering.

5 Treatment Plan

5.1 Patient Preparation

Patients will fast for four hours prior to examination as per joint EANM/EANO/RANO practice guidelines/SNMMI procedure standards for imaging of gliomas using PET with radiolabeled amino acids.

5.2 Dosage and Administration

The imaging agent (FET) will be administered on an outpatient basis. It will be administered intravenously within the PET scanner at the time of imaging. The nominal injected dose will be 4 to 7 mCi \pm 10% of FET per imaging time point. Pediatric doses will be adjusted based upon the patient's weight (dose = [(patient weight in kg)/70 kg] x adult dose). The maximum dose will be 7 mCi, adjusted by weight.

5.2.1 Other Modalities or Procedures

5.2.1.1 PET Imaging

Participants may undergo sedation as required in order to successfully undergo imaging. Sedation or anesthesia will be administered per institutional protocol.

Study participants will undergo the FET PET imaging after all screening and baseline assessments have been completed. The radiopharmaceutical will be administered while the

patient is in the PET scanner, and imaging will last for 40 minutes. Acquired PET data will be reconstructed so that three time points are created:

1. Perfusion: 60-second acquisition that starts immediately when activity is noted in the field of view.
2. Equilibrium: 10-minute acquisition acquired between 10 and 20 minutes after injection.
3. Washout: 10-minute acquisition acquired between 30 and 40 minutes after injection.

Additionally, a 20 minute acquisition will be reconstructed between 20 and 40 minutes after injection to match the analysis performed in Lohmann et al (8).

Each study will be reviewed by a board-certified nuclear medicine physician and neuroradiologist within seven working days of the completion of the study, and a formal report will be dictated. This will be performed separately from the final analysis. The imaging findings on FET PET will be provided to the neurosurgeon and can be used in addition to MRI for planning of biopsy and surgery. For patients who received subsequent surgery, if possible the multi-parametric imaging examination will be used to target 1-4 tissue samples that have distinct metabolic findings for distinguishing recurrent disease from treatment effects.

If imaging is performed on a PET/MRI, a gadolinium-based contrast will be administered. The patient's eGFR will be checked and gadolinium will be administered per radiology department guidelines. The MRI protocol will include the clinical standard MRI. The MRI protocol may also contain research sequences such as novel sequences used for attenuation correction on PET/MRI (ie ZTE or zero echo time) and MRI spectroscopy sequences.

Optional repeat FET PET imaging will be offered to adult patients.

5.3 Monitoring and Toxicity Management

Each patient receiving FET will be evaluable for safety. The safety parameters include vital signs (heart rate and blood pressure) as well as physical findings and spontaneous reports of adverse events reported to the investigator by patients.

6 Study Procedures and Observations

Screening assessments must be performed within 30 days prior to the first dose of investigational product. Any results falling outside of the reference ranges may be repeated at the discretion of the investigator. Treatment or visit delays for public holidays or weather conditions do not constitute a protocol violation.

A written, signed, informed consent form (ICF) and a Health Insurance Portability and Accountability Act (HIPAA) authorization must be obtained before any study-specific assessments are initiated. A copy of the signed ICF will be given to the subject and a copy will be filed in the medical record. The original will be kept on file with the study records.

REDCap will be used to collect data for this study. REDCap is a secure, HIPAA-compliant, web-based system.

6.1.1 Treatment Period

- FET administration and adverse event evaluation
 - Evaluation of adverse events 20 min after completion of imaging, \pm 60 min

- Vital signs
 - 20 min prior to administration of radiotracer, \pm 60 min
 - 20 min after completion of imaging, \pm 60 min
- Confirmation of negative pregnancy test (woman of childbearing potential only)

6.1.2 Follow-up

Patients will be followed up clinically to see if they have undergone biopsy or surgical resection. This will be performed based on standard of care and is not a requirement as part of this protocol. For patients who have not had biopsy or surgical resection, we will review imaging studies performed within six months of the FET PET in order to evaluate change in size as part of the secondary aims.

6.1.3 Optional Study Procedures - Imaging

Optional repeat FET PET imaging will be offered to adult patients. Repeat procedures include:

- FET administration and adverse event evaluation
 - Evaluation of adverse events 20 min after completion of imaging, \pm 60 min

6.2 Prohibited Medications

There are no prohibited medications.

7 Evaluation of Safety

7.1 Definitions

7.1.1 Evaluable for Toxicity

All patients will be evaluable for toxicity from the time of FET administration.

7.1.2 Adverse Event

An adverse event (also known as an adverse experience) is defined as any untoward medical occurrence associated with the use of a drug in humans, whether or not considered drug related. More specifically, an adverse event (can be any unfavorable and unintended sign (e.g., an abnormal laboratory finding), symptom, or disease temporally associated with the use of a drug, without any judgment about causality. An adverse event can arise from any use of the drug (e.g., off-label use, use in combination with another drug) and from any route of administration, formulation, or dose, including an overdose.

7.1.3 Adverse reaction

An adverse reaction is defined as any adverse event caused by the use of a drug. Adverse reactions are a subset of all suspected adverse reactions for which there is reason to conclude that the drug caused the event.

7.1.4 Suspected

A suspected adverse reaction is defined as any adverse event for which there is a reasonable possibility that the drug caused the adverse event. For the purposes of IND safety reporting,

“reasonable possibility” indicates that there is evidence to suggest a causal relationship between the drug and the adverse event. A suspected adverse reaction implies a lesser degree of certainty about causality than an adverse reaction.

7.1.5 Unexpected

An adverse event or suspected adverse reaction is considered unexpected if it is not listed in the investigator brochure or package insert(s), or is not listed at the specificity or severity that has been observed, or, if an investigator brochure is not required or available, is not consistent with the risk information described in the general investigational plan or elsewhere in the current application.

“Unexpected,” as used in this definition, also refers to adverse events or suspected adverse reactions that are mentioned in the investigator brochure as occurring with a class of drugs or as anticipated from the pharmacological properties of the drug, but are not specifically mentioned as occurring with the particular drug under investigation.

Adverse events that would be anticipated to occur as part of the disease process are considered unexpected for the purposes of reporting because they would not be listed in the investigator brochure. For example, a certain number of non-acute deaths in a cancer trial would be anticipated as an outcome of the underlying disease, but such deaths would generally not be listed as a suspected adverse reaction in the investigator brochure.

7.1.6 Serious

An adverse event or suspected adverse reaction is considered serious if, in the view of either the investigator or sponsor, it results in any of the following outcomes:

- Death
- Life-threatening adverse event
- Inpatient hospitalization or prolongation of existing hospitalization
- A persistent or significant incapacity or substantial disruption of the ability to conduct normal life function
- Congenital anomaly/birth defect

Important medical events that may not result in death, are life-threatening, or require hospitalization may be considered serious when, based upon appropriate medical judgment, they may jeopardize the patient or subject and may require medical or surgical intervention to prevent one of the outcomes listed in this definition. Examples of such medical events include allergic bronchospasm requiring intensive treatment in an emergency room or at home, blood dyscrasias or convulsions that do not result in inpatient hospitalization, or the development of drug dependency or drug abuse.

7.1.7 Life-threatening

An adverse event or suspected adverse reaction is considered life-threatening if, in the view of either the investigator or sponsor, its occurrence places the patient or subject at immediate risk of death. It does not include an adverse event or suspected adverse reaction that, had it occurred in a more severe form, might have caused death.

7.2 Recording of an Adverse Event

All grade 3 and above adverse events will be recorded using the NCI CTCAE v4.0. The Investigator will assign attribution of the possible association of the event with use of the investigational drug.

| Relationship | Attribution | Description |
|--|-------------|--|
| Unrelated to investigational drug/intervention | Unrelated | The AE is clearly NOT related to the intervention |
| | Unlikely | The AE is doubtfully related to the intervention |
| Related to investigational drug/intervention | Possible | The AE may be related to the intervention |
| | Probable | The AE is likely related to the intervention |
| | Definite | The AE is clearly related to the intervention |

Signs or symptoms reported as adverse events will be graded and recorded by the Investigator according to the CTCAE. When specific adverse events are not listed in the CTCAE they will be graded by the Investigator as none, mild, moderate or severe according to the following grades and definitions:

| | |
|----------|---|
| Grade 0 | No AE (or within normal limits) |
| Grade 1 | Mild; asymptomatic or mild symptoms; clinical or diagnostic observations only; intervention not indicated |
| Grade 2 | Moderate; minimal, local, or noninvasive intervention (e.g., packing, cautery) indicated; limiting age-appropriate instrumental activities of daily living (ADL) |
| Grade 3: | Severe or medically significant but not immediately life-threatening; hospitalization or prolongation of hospitalization indicated; disabling; limiting self-care ADL |
| Grade 4: | Life-threatening consequences; urgent intervention indicated |
| Grade 5: | Death related to AE |

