2.2 Secondary Objectives

| Secondary Objectives | Endpoints | Time Frame |
|--|---|-----------------|
| 1. To determine if FET PET can differentiate between benign TRC and recurrent glioma in comparison to a histopathological standard of truth. | 
 • Sensitivity of FET PET using a histopathology standard of truth (subject- and lesion-level) • Specificity of FET PET using a histopathology standard of truth (subject and lesion-level) • Positive Predictive Value (PPV) of FET PET using a histopathology standard of truth (subject and lesion-level) • Negative Predictive Value (NPV) of FET PET using a histopathology standard of truth (subject and lesion-level) • Accuracy of FET PET using a histopathology standard of truth (subject and lesion-level) • Misclassification Rate of FET PET using a histopathology standard of truth (subject and lesion-level) | Up to 6 months. |
| 2. To determine if FET PET can differentiate between benign TRC and recurrent glioma in comparison to a CSOT evaluated using estimates other than subject-based sensitivity and specificity. | 
 • Sensitivity of FET PET using a CSOT (lesion-level) • Specificity of FET PET using a CSOT (lesion-level) • PPV of FET PET using a CSOT (subject and lesion-level) • NPV of FET PET using a CSOT (subject and lesion-level) • Accuracy of FET PET using a CSOT (subject and lesion-level) • Misclassification Rate of FET PET using a CSOT (subject and lesion-level) | Up to 6 months. |

| Secondary Objectives | Endpoints | Time Frame |
|---|--|-----------------|
| 3. To assess the safety of FET PET, as determined by treatment emergent adverse events (TEAEs) within 48 hours of FET administration. | Incidence of treatment-emergent adverse events (TEAEs) | Up to 48 hours. |
| 4. To describe the inter-reader variability between 3 independent blinded readers of FET PET images in their assessments of benign TRC versus recurrent glioma. | Fleiss' kappa | N/A |
| 5. To describe intra-reader variability between 3 independent blinded readers of FET PET images in their assessments of benign TRC versus recurrent glioma. | Cohen's kappa | N/A |

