3.1 Adverse Event Monitoring

All Grade 3-5 adverse events (AEs), whether or not considered expected or unexpected and whether or not considered associated with the study intervention or procedure, will be entered into OnCore®, UCSF’s Clinical Trial Management System.

Adverse events are graded according to the Common Terminology Criteria for Adverse Events (CTCAE) as developed and revised by the Common Therapy Evaluation Program (CTEP) of the National Cancer Institute. Adverse events are further given an assignment of attribution or relationship to study intervention or procedure. Attribution categories are:

- **Definite** – clearly related to the study intervention or procedure.
- **Probable** – likely related to study intervention or procedure.
- **Possible** – may be related to study intervention or procedure.
- **Unrelated** – clearly not related to the study intervention or procedure.

All clinically significant adverse events entered into OnCore® will be reviewed on a monthly basis at the Site Committee meetings

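### Section 7.2 gives two conflicting rules on which adverse event grades are recorded, and its opening rule starts at grade 3 while the TEAE endpoint has no grade limit

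*Combined protocol and SAP*

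**What the plan says.** **Endpoint.** Section 2.2, objective 3, is "To assess the safety of FET PET, as determined by treatment emergent adverse events (TEAEs) within 48 hours of FET administration". The endpoint beside it is the incidence of TEAEs. Neither carries a grade restriction.

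**Recording rules that start at grade 3.** Section 7.2 opens with "All grade 3 and above adverse events will be recorded using the NCI CTCAE v4.0". Appendix 2, section 3.1, has a matching rule for entry into OnCore, the institution's trial management system: "All Grade 3-5 adverse events (AEs), whether or not considered expected or unexpected".

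**Recording rule with no floor.** Later in Section 7.2: "Signs or symptoms reported as adverse events will be graded and recorded by the Investigator according to the CTCAE". For events that the CTCAE does not list, "they will be graded by the Investigator as none, mild, moderate or severe according to the following grades and definitions", and the table that follows defines grades 1 and 2.

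**Ascertainment and data system.** Section 5.3 counts among the safety parameters "physical findings and spontaneous reports of adverse events reported to the investigator by patients". The abstract says that patients will be asked about adverse events, and Section 6.1.1 schedules an adverse event check after imaging. Section 6 adds that "REDCap will be used to collect data for this study". None of these mentions grade.

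**Analysis.** Section 9.2.1 defines a safety dataset. Section 9.2.3, on secondary endpoints, does not say how TEAE incidence is tabulated or which grades count.

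**The concern.** An incidence is only as complete as the recording behind it. The endpoint counts TEAEs of every grade, yet the two sentences that promise to record or enter every event of a class both begin at grade 3. The sentence that could cover milder events sits further down the same section and does not refer back to the opening rule.

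Two members of staff could follow 7.2 in good faith and collect different data. One would record every reported symptom. The other would record from grade 3, and the table headed TEAE would then hold grade 3-5 events under an all-grade label. A reader of the results could not tell which had happened.

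Section 1.1 says that the study is meant to supply prospective safety and efficacy data for an NDA. Mild events not written down at the time cannot be reliably recovered later, and no analysis can repair the gap.

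**Working it through.** The plan states no expected TEAE rate, safety sample size or safety precision, so there is no figure of its own to reproduce. The check has two parts.

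**1. The texts side by side**

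| Place | Grades covered | Purpose |
|---|---|---|
| 2.2, objective 3 | no limit | endpoint |
| 7.2, opening sentence | 3 and above | recording |
| 7.2, later sentence and grade table | no floor; grades 1-2 defined | recording and grading |
| Appendix 2, 3.1 | 3-5 | OnCore entry |
| 5.3, 6, 6.1.1, abstract | not stated | eliciting events, data system |

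If the later sentence of 7.2 governs, the opening one adds nothing for reported signs or symptoms. If the opening sentence is a floor, the later one has no effect for grades 1-2. The text does not say which prevails.

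**2. How far the two readings differ**

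Inputs:
- N = 199, the planned enrolment in Section 3.3. The safety set is those who complete the initial scan, so this is approximate.
- Any-grade TEAE rate p: assumed 2%, 5% or 10%.
- Grade 3+ TEAE rate q: assumed 0.05%, 0.25%, 0.5% or 1%.

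The documents give neither rate. Patients are treated as independent.

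Expected patients with a recorded TEAE are N × p if all grades are recorded and N × q if recording starts at grade 3. The chance of recording none is (1 − p)^199 or (1 − q)^199.

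| Reading | Assumed rate | Expected patients | Chance of none |
|---|---|---|---|
| All grades | 2% | 199 × 0.02 = 4.0 | 1.8% |
| All grades | 5% | 199 × 0.05 = 10.0 | 0.004% |
| All grades | 10% | 199 × 0.10 = 19.9 | below 0.0000001% |
| Grade 3+ only | 0.05% | 199 × 0.0005 = 0.1 | 91% |
| Grade 3+ only | 0.25% | 199 × 0.0025 = 0.5 | 61% |
| Grade 3+ only | 0.5% | 199 × 0.005 = 1.0 | 37% |
| Grade 3+ only | 1% | 199 × 0.01 = 2.0 | 14% |

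On the grade 3+ reading, the reported number does not depend on the grade 1-2 rate at all.

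If the result were 0 of 199, the exact two-sided 95% upper limit would be 1 − 0.025^(1/199) = 1.8% (Wilson: 1.9%). On the grade 3+ reading that limit bounds grade 3-5 incidence only. Read as a limit on all TEAEs, it would lie below every any-grade rate assumed here.

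**The case against.** The strongest reply is that the plan never excludes grade 1-2 events. The opening sentence of 7.2 makes a firm commitment for grade 3 and above and is silent about the rest. The later sentence records what patients report without a floor, and defining grades 1 and 2 would serve little purpose if such events were never written down. Section 7.3 follows all adverse events, and Section 5.3 accepts spontaneous reports of any severity. The OnCore rule serves oversight, while study data are held in REDCap with no stated limit, so Appendix 2 does not show that mild events are missing from the dataset. The endpoint is also descriptive and secondary: study success in Section 9.2.2 depends only on sensitivity and specificity.

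Most of this stands. A reader might infer that only grade 3 and above is recorded, and that the trial will therefore report almost no TEAEs whatever the truth. The documents do not support that. The word *only* is not in the text, and how small the reported rate would be depends on a grade 3+ rate that the plan does not give. At 1%, about two patients would still be expected.

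The reply does not remove the inconsistency. The places it cites say how events are elicited, followed and stored. Apart from the later sentence of 7.2, none says which grades are recorded, and nowhere does the plan state that every grade 1-2 TEAE is captured for the endpoint.

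**Conclusion.** The point holds as an inconsistency in the recording rule, not as a stated exclusion of mild events. Section 7.2 contains one rule that starts at grade 3 and one with no floor, and the endpoint needs the second. If the first is applied as a floor, the reported TEAE incidence becomes grade 3-5 incidence. Under assumed rates of 5% for any grade and 0.5% for grade 3+, that is the difference between about 10 and about 1 of 199 patients. The gap changes with the rates assumed, and it disappears if sites already record all grades, which the documents do not settle.

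The primary analysis is untouched. The correction is worth making because the endpoint is meant to support an NDA and the loss could not be reversed, but it ranks below problems that affect the study's main conclusion.

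**What to change.** - Replace the first sentence of 7.2 with a rule that adverse events of all grades within the TEAE window are recorded in the study CRF with grade, onset and attribution.
- Keep the grade 3-5 threshold in Appendix 2, and say that it governs OnCore and DSMC entry only.
- State in Section 9.2.3 that TEAE incidence is reported for any grade and for grade 3+.
- If all grades will not be collected, rename the endpoint *incidence of grade 3-5 TEAEs* in the abstract, in Section 2.2 and wherever it is reported.

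The cost is a few sentences and a little extra data entry for mild events. The adverse event check after imaging is already scheduled (Section 6.1.1 and Appendix 1), so no patients or procedures are added. This settles which grades count. Whether a single check 20 minutes (± 60 minutes) after imaging can cover a 48-hour window is a separate question that this change does not answer.
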